13.0 Withdrawal of Subjects*

A Comparative Study of the Efficacy of Intralesional Sodium Thiosulfate Versus Intralesional Normal Saline for the Treatment of Dystrophic and Idiopathic Calcinosis Cutis, A Double-Blind Randomized Placebo-Controlled Trial

13.1 Subjects will be withdrawn from the research without their consent if they become intolerant to the treatment and/or the researchers determine that they are too nervous, anxious to continue.

13.2 Procedures for orderly termination:

- Subjects may voluntarily terminate their participation in the research at any time by informing a member of the research team.
- A subject may partially withdraw from the study after any of the study visits if the subject is unable or unwilling to do the follow up visits.

13.3 Procedures for subject withdrawal:

- If a subject withdraws or is withdrawn from the study prior to completion, further data collection will be stopped. However, partial data already collected will be used for analysis.
- Orderly termination will proceed at the end of study period for all subjects.

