8.2 Primary and secondary safety endpoints

- Primary safety endpoints: Serious adverse event due to IL STS, will be required to withdraw.
- Secondary safety endpoints:

A Comparative Study of the Efficacy of Intralesional Sodium Thiosulfate Versus Intralesional Normal Saline for the Treatment of Dystrophic and Idiopathic Calcinosis Cutis, A Double-Blind Randomized Placebo-Controlled Trial

- Intolerance to pain associated with injections, will be required to withdraw.
- Vasovagal reaction. If a subject develops a vasovagal reaction, he or she will be given the option to withdraw but will not be required to withdraw.
- If a subject experiences a mild to moderate adverse event he or she will be given the option to withdraw but will not be required to withdraw.

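### Section 13.3 ends all study data collection at withdrawal, so subjects taken off for harm or intolerance have no Week 12 outcome and no documented study follow-up of the event

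*Combined protocol and SAP*

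**What the plan says.** Section 13.3 gives the rule: "If a subject withdraws or is withdrawn from the study prior to completion, further data collection will be stopped". It covers subjects who choose to leave and subjects who are removed. What was recorded before that point is kept: "However, partial data already collected will be used for analysis".

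Two sections make withdrawal compulsory:

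- Section 8.2, primary safety endpoint: "Serious adverse event due to IL STS, will be required to withdraw".
- Section 8.2, secondary safety endpoint: "Intolerance to pain associated with injections, will be required to withdraw".
- Section 13.1: "Subjects will be withdrawn from the research without their consent if they become intolerant to the treatment". The same sentence adds subjects whom the researchers judge too nervous or anxious to go on.

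Section 8.2 makes withdrawal optional after lesser events: "If a subject experiences a mild to moderate adverse event he or she will be given the option to withdraw". A vasovagal reaction carries the same option. Section 13.2 has one intermediate category: "A subject may partially withdraw from the study after any of the study visits". It is meant for subjects who cannot or will not attend follow-up.

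Change in lesion size and change in PGA are primary endpoints, and adverse events are the only secondary endpoint (8.1). Injections are given at Weeks 0, 4 and 8. Week 12 is a 15-minute assessment with no injection (7.1, 9.2). Adverse events are recorded at visits and in one telephone call 48 hours after Visit 1 (9.2).

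**The concern.** Stopping injections and leaving the study are treated as one event. This is a stated rule, so a site that follows the protocol exactly will lose the data. It goes further than respecting withdrawn consent, because it also applies to subjects removed by the investigators who would be willing to come back for measurement.

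Three things are at stake. Week 12 size and PGA describe only the subjects who were not withdrawn, and some of the others are missing because of harm or intolerance. Retained early data combined with missing later data mean that the comparisons across times planned in 11.1 use a different set of subjects at each visit. The adverse event record, which is also the input to the safety review in 12.1, is cut short in the subjects whose events were serious enough to force withdrawal.

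**Working it through.** The plan gives no power, effect size, standard deviation or withdrawal rate, so there is no design figure to reproduce. The check is a reading of the sections together, followed by illustrations under stated assumptions.

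**1. Does any section override 13.3?** None does. Partial withdrawal in 13.2 covers subjects unable or unwilling to attend, which is the opposite of a subject who stops injections but will attend. The investigator's telephone number (9.3) and treatment of research injury (25.1) provide care, not study data.

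**2. The clearest case.** A subject has the third injection at Week 8 and then meets a compulsory criterion. No injection is left to stop. The only remaining study activity is the Week 12 assessment, and 13.3 cancels it.

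**3. Loss per withdrawal.** The plan enrols 12 to obtain 10 eligible subjects, an allowance of 1 − 10/12 = 16.7%. Section 23.2 attributes it to screening failure, so nothing covers loss after treatment starts. Each withdrawal before Week 12 removes 1/10 = 10% of the planned pairs.

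**4. How often (withdrawal rate q assumed, 10 subjects, binomial).** P(at least one) = 1 − (1 − q)^10.

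| q | At least 1 lost | At least 2 lost |
|---|---|---|
| 5% | 40% | 9% |
| 10% | 65% | 26% |
| 20% | 89% | 62% |
| 30% | 97% | 85% |

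**5. How far selection can move a Week 12 result.** Suppose that 4 of 10 STS lesions would respond (assumed; true rate 40%). The extremes are that all lost subjects are non-responders or all are responders.

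| Lost | All non-responders | All responders |
|---|---|---|
| 1 | 4/9 = 44% | 3/9 = 33% |
| 2 | 4/8 = 50% | 2/8 = 25% |
| 3 | 4/7 = 57% | 1/7 = 14% |

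The direction is not known in advance. The saline lesions of the same subjects are lost too, so the difference between lesions can also move either way.

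**6. Would continued follow-up restore power?** Take a paired t-test, two-sided 0.05, with an assumed standardised paired effect of 1.0. From the noncentral t distribution, power is 0.80 with 10 pairs, 0.75 with 9, 0.68 with 8 and 0.60 with 7. The figure of 0.80 returns only if subjects who stop early keep the full effect. By simulation, with 8 subjects at effect 1.0 and 2 early stoppers kept in the analysis:

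| Effect kept by the 2 early stoppers | Power, 10 pairs as allocated |
|---|---|
| none | 0.55 |
| one third | 0.66 |
| two thirds | 0.74 |

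The comparator is 0.68 with the 8 completers alone. Follow-up may therefore raise or lower power.

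**The case against.** Several points on the other side stand.

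- **Power.** A reader might infer that the rule should change because each lost pair costs power. Step 6 shows that this does not follow: power with the early stoppers retained lies on either side of the completers-only figure.
- **A significance floor.** A reader might add that with 5 pairs left, significance is out of reach, since the smallest two-sided signed-rank p is 2/2^5 = 0.0625. Section 11.1 names the Mann-Whitney test, for which 5 lesions per group without ties allow 2/252 = 0.008. Losing 5 or more of 10 is also unlikely: probability 0.0016 at an assumed 10% rate, 0.033 at 20% and 0.15 at 30%.
- **The question asked.** The hypothesis in 1.2 concerns three injections, not the offer of three. A completers' result therefore answers a question that the protocol poses, and should be reported as well.
- **Unequal loss.** Both lesions leave together, so there is no differential loss between STS and saline.
- **Tolerated every injection.** It would be too strong to say that Week 12 covers only such subjects. Those with a mild to moderate event or a vasovagal reaction may stay, and pain scores already recorded are kept.
- **The event is never followed up.** The documents do not show this. The Adverse Event Form is an attachment that cannot be seen here, and clinical care continues. What can be said is that 13.3 provides for no documented study follow-up after withdrawal.

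Withdrawals may also be few, since 14.1 anticipates no major risk and minimal pain. None of this explains why a willing subject should be barred from being measured.

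**Conclusion.** The point holds as a matter of selection and of safety data. Followed as written, 13.3 together with 8.2 and 13.1 removes the Week 12 size and PGA of every subject withdrawn before that visit, and ends the study's adverse event record for the same subjects. The certain size is 10% of the planned pairs per withdrawal. How many will be lost, and which way the results would move, rests on the assumed rates above, because the documents give none. Section 12.1 reviews cumulative adverse events once 5 of 10 subjects have completed. Events up to withdrawal could be included, but anything later would not be recorded, and it is not stated whether withdrawn subjects count towards the 5. This is a cheap improvement that should be made before enrolment, because a missed assessment cannot be recovered. It implies no judgement on which events should end treatment.

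**What to change.** In 13.3 and the consent form, distinguish a subject who stops study injections from one who withdraws consent to follow-up. Then:

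1. Invite every subject who stops injections, for any reason in 8.2 or 13.1, to the remaining scheduled visits for size, PGA, photographs and adverse events.
2. Record any open adverse event until it is resolved or stable.
3. End collection only when the subject withdraws consent to it.
4. Report Week 12 results for all assessed subjects as allocated and, because the hypothesis concerns three injections, also for those who received all three. Give the number assessed at each visit.

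Who stops injections is unchanged. The cost is wording in two documents and at most three visits that are already scheduled (Weeks 4, 8 and 12) for a subject who stops after the first injection. Those visits are uncompensated (22.5) and at the subject's own transport cost (26.1), which the consent form should say. The as-allocated result may be diluted by subjects who had fewer injections, so the second analysis should stand beside it.

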14.0 Risks to Subjects*

14.1 There is no major anticipated risk associated with the study. However, potential risks to the subject include:

- Discomfort and minimal pain upon injection and infiltration of STS or normal saline.
- Minimal (<27%) risk of nausea and vomiting¹⁵
- Low risk of hypotension, headache, disorientation¹⁵
- Negligible bleeding or bruising
- Negligible risk of infection

The procedures in this research are known to hurt a pregnancy or fetus in the following ways:

Sodium Thiosulfate Injection is Pregnancy Category C. There are no adequate and well-controlled studies in pregnant women. Sodium Thiosulfate Injection should be used during pregnancy only if the potential benefit justifies the potential risk to the fetus.

There are no reported epidemiological studies of congenital anomalies in infants born to women treated with sodium thiosulfate during pregnancy. In animal studies, there are no teratogenic effects in offspring of hamsters treated during pregnancy with sodium thiosulfate in doses similar to those given intravenously to treat cyanide poisoning in humans. Other studies suggest that treatment with sodium thiosulfate ameliorates the teratogenic effects of maternal cyanide poisoning in hamsters. In other studies, sodium thiosulfate was not embryotoxic or teratogenic in mice, rats, hamsters, or rabbits at maternal doses of up to 550, 400, 400 and 580 mg/kg/day, respectively.

15.0 Potential Benefits to Subjects*

15.1 Potential benefits to subjects include:

- Possible improvement of cutaneous calcinosis lesions.

A Comparative Study of the Efficacy of Intralesional Sodium Thiosulfate Versus Intralesional Normal Saline for the Treatment of Dystrophic and Idiopathic Calcinosis Cutis, A Double-Blind Randomized Placebo-Controlled Trial

16.0 Vulnerable Populations*

16.1 This study does not involve individual who are vulnerable to coercion or undue influence.

17.0 Community-Based Participatory Research*

17.1 This is not community-based participatory research.

18.0 Sharing of Results with Subjects*

18.1 There are no plans to share results with subjects.

19.0 Setting

19.1 Research will be conducted at UCF Health:

- Potential subjects will be identified and recruited at both the UCF Health clinic in Lake Nona and the UCF Health clinic on [name].
- Screening, enrollment and the initial/baseline study visit will take place at the UCF Health clinic in Lake Nona. Follow up study visits will take place at the UCF Health clinic in Lake Nona.
- There will not be a community advisory board.

20.0 Resources Available

20.1 [name] has significant prior experience conducting research, knowledge of the regulations and customs at UCF Health, and works regularly with patients performing dermatologic surgery. All injections will be administered by [name]. [name] has extensive experience conducting clinical research. In addition, the medical students involved in the project will be able to help significantly. Through the FIRE project [name] will be able to assist with data analysis.

20.2 Resources available to conduct research:

- The study's small sample size (N=10) makes it likely that the required number of subjects will be recruited in less than 8 months. [name] combined see more than half this number of patients with calcinosis cutis annually. In addition, the rheumatologists at UCF Health see at least as many patients with calcinosis cutis. Finally, recruiting through the local dermatology society and advertising should supplement the numbers needed to complete the study.
- Research will be conducted during [name] administrative time or on the weekend.
- The study will be will be conducted at the UCF Health Clinic, see section 19. Setting.
- While the chances of a research related injury are extremely rare, subjects will be required to have health insurance in order to participate in this study. Treatment for research related injury will be made available,

A Comparative Study of the Efficacy of Intralesional Sodium Thiosulfate Versus Intralesional Normal Saline for the Treatment of Dystrophic and Idiopathic Calcinosis Cutis, A Double-Blind Randomized Placebo-Controlled Trial

however costs associated with this treatment will be billed to the subject's insurance company. Costs not covered by the subject's insurance company will be the subject's responsibility.

- All individuals assisting in the research study will be provided a copy of the IRB-approved protocol and given the opportunity to meet with the principal investigator before recruitment begins. The principal investigator, [name], will be responsible for informing all research staff of their research-related duties during a personal meeting or via phone or email. The contact information of the principal investigator and co-principal investigator will be distributed to all research staff and the subjects.

21.0 Prior Approvals

21.1 Approval from the medical director and the HIPAA privacy officer of UCF Health will be obtained prior to commencing research.

22.0 Recruitment Methods

22.1 The research team will start recruitment shortly after IRB approval and the sodium thiosulfate has been received. Patients with a diagnosis of calcinosis cutis will be recruited from the UCF Health Clinic during a patient's visit (medical records will not be searched for patients with a diagnosis of calcinosis cutis) and through advertising on the UCF Health website and within the UCF Health clinic.

22.2 The primary source of subjects will be patients at the UCF Health Clinic and people in the greater Orlando area. This represents a large pool of potential subjects from which to recruit.

22.3 [name] and [name] will rely on prior labs, pathology reports, and physical examination to determine if the participant has a diagnosis of calcinosis cutis. As stated, medical records will not be searched for patients with a diagnosis of calcinosis cutis.

22.4 An e-mail and within clinic advertisement may be used to recruit patients (see attached Advertisements). This is a small paragraph describing the study. This text may be displayed in the UCF Health clinic, to other providers at UCF Health or members of the local dermatology society. In addition, a similar small paragraph describing the study will be posted on the UCF Health website (see attached Advertisements).

22.5 Subjects will not be compensated for their time.

23.0 Local Number of Subjects

23.1 We plan to enroll approximately 12 subjects.

A Comparative Study of the Efficacy of Intralesional Sodium Thiosulfate Versus Intralesional Normal Saline for the Treatment of Dystrophic and Idiopathic Calcinosis Cutis, A Double-Blind Randomized Placebo-Controlled Trial

23.2 We anticipate most subjects that are enrolled to be successfully screened. There may be a few subjects that will fail screening due to failing urine pregnancy testing. Given this, it may be that 12 subjects need to be enrolled and screened to obtain 10 eligible subjects.

24.0 Provisions to Protect the Privacy Interests of Subjects

24.1 Subjects will be in the same general vicinity during the study and will be recruited from the UCF Health Clinic. Therefore, there will be the possibility that subjects may know and recognize each other.

24.2 Prior to enrollment subjects will be made aware of this possibility and if unacceptable, will be given the option to decline to participate.

24.3 All investigators will have access to all of the information collected on the subjects. The “Subject ID Assignment Log” will be kept in a separate folder so that investigators will only have access to identifiable information if needed for data entry or if there is a data discrepancy. Only de-identified data will be exported and used for data analysis.

25.0 Compensation for Research-Related Injury

25.1 While the chances of a research related injury are extremely rare, subjects will be required to have health insurance in order to participate in this study. Treatment for research related injury will be made available, however costs associated with this treatment will be billed to the subject’s insurance company. Costs not covered by subject’s insurance company will be the subject’s responsibility.

26.0 Economic Burden to Subjects

26.1 Subjects have to give his or her time (approximately 5 hours) and bear any transportation costs (gas, tolls, etc.). If the subject’s health insurance does not cover the costs for the treatment related injury, the subjects will be billed for the treatment. There are no other expected costs that subjects will incur as a result of participating in the study.

27.0 Consent Process

27.1 Consent process:

- The consent process will take place in person at the UCF Health clinic in Lake Nona.
- Subjects will be given the option of picking up the consent and HIPAA authorization prior to participation to discuss with their primary care physician, significant other, etc., to help minimize the possibility of

A Comparative Study of the Efficacy of Intralesional Sodium Thiosulfate Versus Intralesional Normal Saline for the Treatment of Dystrophic and Idiopathic Calcinosis Cutis, A Double-Blind Randomized Placebo-Controlled Trial

coercion or undue influence. Subjects will be able to wait however long they desire after obtaining the study information and before signing the consent and HIPAA authorization. However, if the study is completed before the subject chooses to sign the consent then they will not be allowed to participate.

- Subjects may voluntarily terminate their participation in the research at any time by informing a member of the research team. Other than the initial informed consent no other formal process will be done to document ongoing consent.
- The UCF “SOP: Informed Consent Process for Research (HRP-090)” will be followed.
- The consent process will be documented in writing on the Informed Consent and HIPAA Authorization. The investigator will describe the details of the study and answer any questions the subject may have about the study. Subjects will be given an informed consent and HIPAA authorization for the study and the primary investigator’s contact information. Those subjects who express interest in the study will be required to sign the Informed Consent form and HIPAA authorization to ensure that there is no coercion in the study.

28.0 Process to Document Consent in Writing

28.1 The UCF “SOP: Written Documentation of Consent (HRP-091)” will be followed.

28.2 All subjects will be required to complete and sign the informed written consent document and HIPAA Authorization to ensure that there is no coercion in the study. The informed consent documents will be signed both by the subject and by the principal investigator (see attached “Informed Consent” and “HIPAA authorization”).

